1.5.2 Rationale for Dose and Dose Regimen Selection

In Dose-Determination Phase Segment 1, the starting dose of CORT125281 will be 180 mg BID. The starting dose of CORT125281 is based on the following: (1) the anticipated safe exposure based on nonclinical toxicology and the ongoing Phase 1 SAD/MAD study in healthy subjects, (2) the biologically active dose range based on the rat cortisone-induced model of insulin resistance, and (3) the anticipated efficacious dose based on nonclinical mouse models (see Section 1.3.1 for a detailed summary).

At the time of initiation of this study, Study CORT125281-600 was an ongoing Phase 1 SAD/MAD study to assess the tolerability and PK of CORT125281 in the absence of other medications or comorbidities, define the pharmacologically active dose range, and assess the potential of CORT125281 for drug-drug interactions. No safety signals had been identified. Analysis of the available PK data from Study CORT125281-600 indicated that CORT125281 exposure is dose-proportionate from 120 to 720 mg based on both C_{max} and AUC_{0-24} .

Therefore, the predicted accumulation is minimal on repeat daily dosing. CORT125281 mean AUC_{0-24} following single-agent administration ranged from 217.4 ng•h/mL (40 mg dose) to 7199 ng•h/mL (720 mg dose). Based on the human PK data and modeling, a CORT125281 dose of 180 mg BID would result in an estimated AUC_{0-24} of 4200 ng•h/mL. The NOAEL following

28 days of oral gavage administration of CORT125281 to rats was 30 mg/kg/day in both sexes, with a corresponding exposure of 56,142 ng•h/mL in female rats, and 57,533 ng•h/mL in male rats (AUC_{0-24}). The estimated exposure of the 180 mg BID starting dose (4200 ng•h/mL) provides a 10-fold safety factor from the NOAEL exposure in the rat of 57,533 ng•h/mL.

Efficacy in nonclinical mouse models in combination with enzalutamide was observed at 20 mg/kg/day administered using the intraperitoneal route. In the mouse xenograft model, efficacy was observed at a minimum concentration (C_{min}) of 110 ng/mL; based on simulated human PK profiles, a CORT125281 dose of 360 mg BID would provide a 12-hour C_{min} of 137 ng/mL. In the cortisone-induced model of insulin resistance, the minimum anticipated biological effect level is 6 mg/kg/day in the rat with an estimated C_{max} of ~600 ng/mL (see Section 1.3.1.1.3). In Study CORT125281-600, a CORT125281 dose of 360 mg provided an observed mean C_{max} of 688 ± 120 ng/mL. The starting dose of CORT125281 of 180 mg BID is within the anticipated biologically effective dose range and will allow characterization of tolerability, PD, and preliminary efficacy across a range of doses during the Dose-Determination Phase.

The starting dose of enzalutamide in Dose-Determination Phase Segment 1 will be 160 mg QD. At initial clinical doses of CORT125281, the free drug concentrations are not expected to cause a meaningful increase in exposure to enzalutamide and metabolites; thus, the indicated dose of enzalutamide has been selected as the starting dose (Section 1.4; Xtandi USPI 2019). In Dose-Determination Segment 2, patients will continue taking enzalutamide at the patient's currently tolerated dose at baseline. In the Expansion Phase, patients will take enzalutamide 160 mg if not currently receiving enzalutamide or will take their currently tolerated dose of at baseline (if enzalutamide is ongoing from immediately preceding line of therapy).

In Dose-Determination Phase Segment 2, an alternative dosing strategy of upward titration from a starting dose of CORT125281 240 mg QD to 320 mg QD will be evaluated in a blinded manner. The effects of GCs and GC sensitivity can vary dramatically from individual to individual. Similarly, the PD effect of a GR antagonist for a given dose or exposure varies among individuals. In order to optimize the dose for each individual in the presence of by-patient variability in PK and sensitivity to GR antagonism and to minimize the exposure of individuals to potentially suboptimal doses, intra-patient dose escalation of CORT125281 is deemed appropriate.

Both the starting dose of CORT125281 240 mg QD under fed conditions and the highest dose of CORT125281 320 mg QD under fed conditions have been selected and deemed to be appropriate for Segment 2 based on the results from Dose-Determination Phase Segment 1 and the Phase 1 Study CORT125281-600 in healthy adult participants. Specifically, the plasma concentrations of CORT125281 observed in Segment 1 of this study, in combination with the decrease in CORT125281 C_{max} observed in Study CORT125281-600 following fed administration versus fasted administration, indicate that a targeted CORT125281 dose range of 240 mg to 320 mg administered QD under fed conditions will provide CORT125281 exposures (AUC_{0-24} and C_{max}) within the protocol-specified safety rule (Section 5.3) of 1.5-fold the previous dose level.

Additionally, the CORT125281 dose range to be evaluated in Segment 2 is 240 mg QD to 320 mg QD and is expected to yield pharmacodynamically active exposures resulting in GR antagonism, based on the PD data from Study CORT125281-600, in which subjects were

administered prednisone 25 mg with or without CORT125281. The biological activities of the GR agonist (prednisone) and antagonist (CORT125281) were assessed by measuring messenger ribonucleic acid (mRNA) expression of GC-modulated pathways in whole blood. A single 360-mg dose antagonized the biological activity of prednisone when administered with food. The same single CORT125281 360-mg dose under fasted conditions showed less antagonism. Food effects on the activity of prednisone alone were negligible. Given these data, it is anticipated that continuous dosing of CORT125281 240 to 320 mg under fed conditions will result in measurable GR antagonism.

The dose regimen selection of CORT125281 in combination with enzalutamide in subsequent cohorts and the selection of the RD for the expansion cohorts and future development will be based upon PK and safety data collected during the Dose-Determination Phase of the study and reviewed by the Data Review Committee (DRC).

1.5.3 Rationale for Patient Selection

Patients with mCRPC who have received no more than 2 prior lines of cytotoxic chemotherapy will be enrolled to this Phase 1/2a study. This population is consistent with the indication for enzalutamide. Patients who have previously received enzalutamide will be allowed to participate, as GR antagonism is intended to target one of the mechanisms of resistance to enzalutamide therapy.

1.6 Benefits and Risks

CORT125281 is a selective GR antagonist that is being developed for the treatment of mCRPC in combination with enzalutamide. GR activation has been identified as a mechanism of resistance to therapies that target the AR ([Arora et al. 2013](#); [Isikbay et al. 2014](#)). The ability of a GR antagonist to restore sensitivity to enzalutamide has been reported ([Arora et al. 2013](#)) and GR depletion has been reported to delay CRPC formation in nonclinical models ([Isikbay et al. 2014](#)). In a castrated mouse xenograft model of CRPC, CORT125281 impaired tumor growth over castration alone, and the combination of CORT125281 and enzalutamide impaired tumor growth over enzalutamide alone. Thus, CORT125281 is anticipated to provide clinical benefit in CRPC in combination with enzalutamide.

The principal risk identified from the nonclinical data was to the male reproductive tract and included bilateral degeneration of the spermatocytes and spermatids and oligospermia/germ cell debris in the testes. This risk does not preclude the use of CORT125281 in the intended target population of male patients with CRPC. Potential adverse effects of CORT125281, based on the pharmacological effect of a GR antagonist, may include signs and symptoms consistent with excessive GR blockade. Patients with conditions that require chronic or frequent corticosteroids will be excluded. Based upon clinical data with other GR antagonists (mifepristone and CORT125134), potential risks of CORT125281 include nausea, fatigue, headache, hypokalemia, arthralgia, vomiting, peripheral edema, hypertension, and musculoskeletal pain.

Based upon clinical data for other GR antagonists (such as mifepristone and relacorilant), potential risks of CORT125281 include nausea, fatigue, headache, arthralgia, vomiting, peripheral edema, and musculoskeletal pain. Within the Phase 1 Study CORT125281-600 in healthy subjects receiving multiple dosing with CORT125281, the most frequent

treatment-related TEAEs were in the following SOC: gastrointestinal system disorders, ear and labyrinth disorders, nervous system disorders, and musculoskeletal and connective tissue disorders. Although the number of events is too small to determine an association with CORT125281, treatment-related gastrointestinal disorders and musculoskeletal and connective tissue disorders were reported only by subjects treated with CORT125281 and with a generally increasing incidence with dose. Thus, in this study, no additional potential risks of CORT125281 were identified. No patterns of TEAEs were observed in healthy subjects receiving single doses of CORT125281 (Studies CORT125281-600 and CORT125281-602).

In the current study, CORT125281 will be given in combination with enzalutamide. Enzalutamide has been demonstrated to have survival benefit in patients with CRPC ([Xtandi USPI 2019](#) and [Xtandi SmPC 2019](#)). The most common adverse reactions of enzalutamide ($\geq 10\%$) that occur more frequently ($\geq 2\%$ over placebo) in patients treated with enzalutamide are asthenia/fatigue, back pain, hot flush, constipation, arthralgia, decreased appetite, diarrhea, and hypertension ([Xtandi USPI 2019](#)). In general, enzalutamide is well-tolerated and enzalutamide-related AEs of Grade 3 or greater are uncommon. The most common AE is fatigue (34%36%), but this rarely reaches Grade 3 or greater. Seizure has been reported in patients receiving enzalutamide ($<1\%$), primarily in patients with predisposing factors that could lower the threshold for seizure. Thus, patients at increased risk for seizure will be excluded from this study and medications that could lower the seizure threshold (such as olanzapine, prochlorperazine, or methylphenidate) should be avoided. Based upon the mechanism of action, enzalutamide and CORT125281 are not anticipated to have overlapping toxicities.

Patients will be closely monitored during the study; standard safety tests will be performed at regular intervals; and samples collected to determine standard PK parameters for CORT125281, enzalutamide, and their major metabolites. Concurrent therapy with strong inhibitors or inducers of CYP3A4 or CYP2C8 or with sensitive substrates of CYP3A4, CYP2C9, or CYP2C19 will be prohibited during the study treatment, consistent with the enzalutamide label and with consideration of potential drug-drug interactions between enzalutamide and CORT125281.

Although animal toxicity studies do not always predict the potential human toxicities of a new drug candidate, the completed GLP toxicity studies support the probable satisfactory tolerance of CORT125281 in the dose range to be investigated in this study.

2 OBJECTIVES

2.1 Primary Objective

The primary objective of this study is to determine the MTD and/or biologically active doses of CORT125281 in combination with enzalutamide to identify the RD for Phase 2 studies.

2.2 Secondary Objectives

The secondary objectives of this study are to:

- Evaluate the safety and tolerability of CORT125281 in combination with enzalutamide
- Characterize the preliminary efficacy of CORT125281 in combination with enzalutamide by determining the objective response rate (ORR), proportion of patients with a reduction in prostate-specific antigen (PSA) level by >50%, time to a symptomatic skeletal event (SSE), radiographic progression-free survival (rPFS), including the proportion of patients who are progression-free at 4, 6, and 12 months, duration of response (DOR), and overall survival
- Assess time to biochemical (PSA progression) bone disease progression, and clinical progression, including the proportion of patients who are progression-free at 4, 6, and 12 months
- Determine the PK profile of CORT125281 and enzalutamide, when co-administered
- Determine the effect of food on the PK of CORT125281

2.3 Exploratory Objectives

Exploratory objectives of this study are to:

- Evaluate the effects of CORT125281 in combination with enzalutamide on the hypothalamic pituitary-adrenal (HPA) axis, including assessments of:
 - Urinary free cortisol (UFC)
 - Serum cortisol
 - Plasma adrenocorticotrophic hormone (ACTH)
- Explore the antitumor activity of the combination of CORT125281 and enzalutamide by line of therapy and in specific sub-sets of disease, including:
 - GR positive versus GR negative, by tumor immunohistochemistry [IHC] and/or circulating tumor cells [CTCs]
 - Androgen-receptor splice variant 7 messenger RNA (ARV7) status
 - Systemic antagonism of cortisol activity as assessed by whole blood transcriptional profiling
- Assess change in PSA
- Conduct correlative analyses of exposure-response for measures of efficacy and changes in GC-modulated pathways, ACTH/cortisol, or other PD markers
- Assess the effect of the pharmacogenomics polymorphisms of the cytochrome P450 pathway on PK and PD parameters (Dose-Determination Phase Segment 1 only)
- Explore the effects of CORT125281 and enzalutamide on patient-reported outcomes (PRO) and quality of life (QoL)

3 STUDY DESIGN

3.1 Overall Design

[figure not shown]
This is a Phase 1/2a, dose-determination and expansion study conducted in patients with mCRPC to evaluate the safety, tolerability, PK, PD, and preliminary efficacy of CORT125281 in combination with enzalutamide; and to identify the RD.

The study consists of the following phases:

- Dose-Determination Phase (Phase 1):
 - Segment 1 (Open-Label, Twice Daily CORT125281): Patients enrolled in this segment will take CORT125281 BID in combination with enzalutamide QD. The starting dose in this segment of the study for CORT125281 is 180 mg BID, with subsequent dose cohorts to be determined based DRC review of tolerability and PK data. Enzalutamide will be administered at a starting dose of 160 mg QD, with subsequent dosing to be determined based upon PK.
 - Segment 2 (Double-Blind, Once Daily CORT125281 Under Fed Conditions): Patients in this segment will be randomized in a 3:1 ratio to Arm A (enzalutamide + titrated dose of CORT125281) and Arm B (enzalutamide + CORT125281 240 mg). All patients will take CORT125281 QD with food. Enzalutamide will be continued at the patient's currently tolerated dose through the Screening Period and the initiation of CORT125281. The DRC will review the frequency of dose-limiting toxicities (DLTs), the DLT rate (number of DLTs per week [7-day period] during the DLT-evaluation period), and overall tolerability in their assessment of the dose titration regimen as the Phase 2 RD.
- Expansion Phase (Phase 2a, CORT125281 at the RD Under Fed Conditions): Once the RD has been determined in the Dose-Determination Phase, the following cohorts will be enrolled and treated with CORT125281 (with the RD regimen, under fed conditions) + enzalutamide. The DRC may elect to expand more than 1 dose level, if needed, to better define the RD:
 - Abi-Resistant Cohort: Patients who have progressed during treatment with abiraterone and no other AR-blocking therapies
 - ARant-Resistant Cohort: Patients who have progressed during treatment with enzalutamide or second-generation AR-blocking therapies.

The overall study design is presented in [Figure 2](#).

Figure 2 CORT125281-601 Study Schematic

AR, androgen receptor; BID, twice daily; DLT, dose-limiting toxicity; DRC, Data Review Committee; MTD, maximum tolerated dose; PD, pharmacodynamic; PK, pharmacokinetic; QD, once daily.

^a. The DRC will review the safety, PK, and PD data from Dose-Determination Phase Segment 1 once a minimum of 3 evaluable patients have completed the DLT-evaluation period (Section 5.4.1).

^b. Enzalutamide will be at the dose currently tolerated by the patient at the time of Screening.

^c. The investigational agent will be increased in 40-mg increments every 2 weeks, as tolerated, with CORT125281 to a maximum dose of 320 mg QD under fed conditions (Arm A) or with placebo (Arm B) to maintain a CORT125281 dose of 240 mg QD under fed conditions (Table 8).

^d. After the DRC meeting for Dose-Determination Segment 2, patients initially randomized to Arm B will have their CORT125281 dose escalated per the recommended Phase 2 regimen.

Patients will participate in the following study periods:

- **Screening Period** will take place within 28 days before the first dose of study treatment
- **Lead-In Period:**
 - Dose-Determination Phase Segment 1: Enzalutamide monotherapy for 28 days
 - Dose-Determination Phase Segment 2: No Lead-In Period
 - Expansion Phase:
 - Food-Effect Subcohort: A single dose of CORT125281 under fasting conditions on Cycle 1 Day -7, and a single dose of CORT125281 30 minutes after a standard breakfast on Cycle 1 Day 1
 - Non-Food-Effect Patients: No Lead-In Period
- **Combination Treatment Period:** Patients will take combination treatment (CORT125281 and enzalutamide) until reaching disease progression, experiencing unmanageable toxicity, or until other treatment discontinuation criteria are met. Patients will continue assessments per the Schedule of Assessments (SoA) for the Combination Treatment Period until both CORT125281 and enzalutamide are discontinued.
- **Follow-Up Period:** Patients will return for a Post-Treatment Follow-Up Visit (End-of-Treatment [EOT] +30 Days Visit) 30 days after their final dose of CORT125281 or enzalutamide, whichever is later. After this, patients will continue to be followed for progression, information on subsequent anticancer therapies (start and end date and response), and survival.

PK, PD, safety, PRO and QoL evaluations will be performed throughout along with preliminary evaluations of antitumor activity as shown in the SoAs ([Appendix A](#)).

Dose evaluation will be guided by safety and PK profiles. Safety will be assessed by review of AEs, including DLTs; clinical laboratory tests, and vital signs. Anticancer activity will be evaluated using bone scan and computed tomography (CT) of the chest, abdomen, and pelvis, per Prostate Cancer Clinical Trials Working Group 3 (PCWG3).

The recommendations of the PCWG3 will be used to determine response ([Scher et al. 2016](#)). Tumor assessments will include ^{99m}Tc-methylene diphosphonate radionuclide bone scintigraphy and CT of the chest, abdomen, and pelvis within 28 days before the first dose of enzalutamide (for Dose-Determination Phase Segment 1) and/or CORT125281 (for Dose-Determination Phase Segment 2 and Expansion Phase) and at intervals of 8 weeks after the first dose of study treatment for the first 24 weeks. Thereafter, tumor assessments will occur at intervals of 12 weeks until disease progression. Objective responses will be confirmed no less than 4 weeks after the criteria for response are first met (if possible, 4–6 weeks). PSA, alkaline phosphatase (ALP), and lactic dehydrogenase (LDH) will be assessed at the Baseline/Screening Visit and Day 1 of each cycle. Results will be documented in the electronic case report form (eCRF). Tumor assessments will be documented until disease progression. Documentation of overall survival including subsequent therapies with duration and response will continue every 4 months until 2 years from the date that the last patient enrolls in the study or until all patients have completed follow-up for radiographic disease progression (whichever is later).

3.1.1 Dose-Determination Phase (Phase 1)

3.1.1.1 Dose-Determination Phase Segment 1 (Open-Label)

Segment 1 of the Dose-Determination Phase is designed to determine DLTs, the MTD/biologically active doses, and the RD of CORT125281 administered daily in combination with enzalutamide in patients with mCRPC. Each cohort must include a minimum of 3 evaluable patients, but can enroll up to 9 patients for dose optimization and selection of the RD. Within each cohort, a sentinel group of 3 patients will be dosed initially, with a minimum of one day between Cycle 1 Day 1 for each patient. Dosing of the remaining patients with CORT125281 + enzalutamide will only proceed after satisfactory review of safety data (excluding laboratory safety tests) from the sentinel group collected up to 24 hours after the first dose of CORT125281 and enzalutamide. The DRC may make the recommendation to adjust the size of a cohort to more than 9 patients to further evaluate a given dose cohort, (eg, based on PK data or tolerability). Dose escalation and dose-finding procedures are described in Section 5.4.

Each patient will begin the Dose-Determination Phase Segment 1 with enzalutamide monotherapy. The DRC may elect to discontinue the Lead-In Period for future cohorts, once the RD of enzalutamide is determined.

After completion of the Lead-In Period, patients will begin the Combination Treatment Period and receive enzalutamide + CORT125281. CORT125281 will be dosed daily starting at 180 mg BID (Cohort 1). Subsequent patients will be enrolled and dosed similarly, with the doses of CORT125281 and enzalutamide for each cohort to be determined based upon the tolerability, PK, and dose escalation/de-escalation rules.

3.1.1.2 Dose-Determination Phase Segment 2 (Double-Blind)

Segment 2 of the Dose-Determination Phase is randomized and double blinded for dose titration with respect to CORT125281 in combination with enzalutamide.

Approximately 20 patients will be enrolled to achieve 16 DLT-evaluable patients randomized in a 3:1 ratio to receive CORT125281 in combination with enzalutamide either with the starting dose of CORT125281 240 mg QD with dose titration to 320 mg QD (N=12; Arm A) or with the starting dose of CORT125281 240 mg QD, without an increase of the active dose (N=4; Arm B), but with the addition of placebo capsules. All doses of CORT125281 should be taken with food.

3.1.2 Expansion Phase (Phase 2a)

Once the RD has been determined in the Dose-Determination Phase, the following cohorts will be enrolled in the Expansion Phase and treated with CORT125281 + enzalutamide according to the RD regimen. The DRC may elect to expand more than 1 dose level, if needed, to better define the RD.

- Abi-Resistant Cohort: Patients who have progressed during treatment with abiraterone and no other AR-blocking therapies (N~20)
 - Food-Effect Subcohort: The effect of food on the PK of CORT125281 will be evaluated in 10 patients enrolled to the Abi-Resistant Cohort. These 10 patients will have a 7-day Lead-In Period as follows:

- Day -7: Single oral dose of CORT125281 administered under fasting conditions
- Day 1: Single oral dose of CORT125281 administered 30 minutes after a standard breakfast. These patients will initiate enzalutamide on Cycle 1 Day 2 to avoid confounding the assessment of the effect of food on CORT125281 PK

Patients in the Abi-Resistant Cohort who do not participate in the food-effect study will not have a Lead-In Period.

- ARant-Resistant Cohort: Patients who have progressed during treatment with enzalutamide or second-generation AR-blocking therapies (N≈20). Note: Patients in the ARant-Resistant Cohort will not have a Lead-In Period.

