1.3.2.1 Clinical Update

As of 18 February 2020, two Phase 1 studies (CORT125281-600 and CORT125281-602) have completed with CORT125281 in healthy subjects, and data are available for 12 patients who have received CORT125281 in combination with enzalutamide in CORT125281-601. This information is briefly summarized below.

Please refer to the most recent CORT125281 IB for further details related to clinical experience with CORT125281 and current safety information.

CORT125281-600

This was the first-in-human study of CORT125281. The study consisted of separate SAD and MAD phases. The first dose level in the MAD part of the study was 120 mg daily. PK parameters at this dose level supported the rationale for administering CORT125281 twice daily (BID), which was employed for the next 2 cohorts (180 mg and 240 mg BID). However, with repeated dosing at these dose levels, a slower terminal elimination phase became apparent and, in the final cohort, an intermediate once daily (QD) dose (360 mg) was evaluated to explore whether this regimen could be used in future studies.

Within-subject comparisons of CORT125281 PK after administration of a single dose of 360 mg CORT125281 under fed and fasted conditions were possible in 3 subjects. The median T_{max} of CORT125281 was 4.08 hours in the fed state and 2.00 hours in the fasted state. The geometric mean C_{max} of CORT125281 was approximately 47% lower under fed versus fasted conditions, while the AUC of CORT125281 was similar when dosed fed or fasted. PK parameters were calculated for multiple doses of CORT125281. Following QD or BID administration of CORT125281 for 14 days, the plasma concentrations of CORT125281 increased at each dose level with repeated dosing, with an approximately 2- to 4-fold increase in exposure. The greatest accumulation in CORT125281 concentrations upon multiple dosing was observed following dosing with CORT125281 240 mg BID. Additionally, CORT125281 plasma concentrations increased in a greater-than-dose-proportional manner between CORT125281 120 mg QD and 360 mg QD, and between CORT125281 180 mg BID and 240 mg BID.

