5.11 Method of Treatment Assignment and Randomization

5.11.1 Dose-Determination Phase Segment 1 and Expansion Phase

Dose-Determination Phase Segment 1 and the Expansion Phase are open label. No randomization or allocation methods will be used in these parts of the study.

5.11.2 Dose-Determination Phase Segment 2

All patients enrolled in Dose-Determination Phase Segment 2 will be centrally assigned to randomized study treatment using interactive response technology (IRT). Before the study is initiated, the log-in information and directions for the IRT will be provided to each site.

Once Screening procedures are complete eligible patients will be randomized in a 3:1 ratio to Arm A (enzalutamide + titrated dose of CORT125281 [240 mg to 320 mg]) and Arm B (enzalutamide + CORT125281 240 mg).

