The PK of CORT125281, the natural log (ln) transformed C_{max}, AUC_{0-t}, and AUC_{inf}, and other PK parameters will be analyzed by analysis of variance (ANOVA) adjusted for food effect and other potential factors that may influence the outcome. The fed state versus fasted state comparison for C_{max}, AUC_{0-t}, and AUC_{inf} will be carried out using 90% CIs for the ratios of these parameters based on the models. If the 90% CIs are contained within the limits 0.80 to 1.25, lack of substantial food effect will be inferred. The T_{max} values between the fed and fasted state will be compared using non-parametric tests.

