The effect of food on the PK of exicorilant will be evaluated in the first 10 patients enrolled in Cohort A of the Expansion phase. Mean time of maximum plasma concentration (T_{\max}) will be compared in this Subcohort of patients under fed and fasting conditions, using a nonparametric test for dependent samples. The relationship of log transformed PK parameters C_{\max} , $AUC_{0-\text{last}}$, and $AUC_{0-\text{inf}}$ will be assessed with food using unadjusted and adjusted linear regression models that control for potential confounders. From these models, least-squares (LS) means, LS mean difference between fed and fasted conditions, and associated CIs will be obtained on the natural log scale. Transformed back from the logarithmic scale via exponentiation, ratios of geometric means under the two conditions and CIs will be estimated and presented. If the obtained 90% CIs for all three PK parameters fall outside the 0.80 – 1.25 range, a significant relationship between food effect and exicorilant will be concluded.

12. Pharmacodynamics and Pharmacogenomic Analyses

Biological samples (e.g., blood, plasma, serum, or tumor tissue) will be obtained from the Safety population for analysis during the study as well as for future analysis.

Summaries of actual values and changes from baseline in ACTH and serum cortisol will be presented by treatment regimen dose group, by arm and overall, for each parameter and assessment time point. Fold change in log2 scale from Baseline will be calculated as $(\log_2(\text{post-baseline measurement}) - \log_2(\text{baseline measurement})) / \log_2(\text{baseline measurement})$.

13. Change from Analyses Planned in Protocol

Definition of treatment emergent is updated from the protocol to be consistent with the definition of safety population (all patients who received at least one dose of exicorilant.) Per SAP Section 7.2 the treatment-emergent period is updated to be defined as the period of time from the date and time of the first dose of exicorilant (instead of study treatment) through 30 days after the last dose of study drug (exicorilant or enzalutamide whichever is later).

Definition of baseline is also updated from the protocol. Baseline is defined as the last measurement collected before the first dose of exicorilant (instead of exicorilant or on-study enzalutamide, whichever is earlier).

14. References

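### Every food-effect patient is dosed fasted first and fed second, so the fed/fasted ratio cannot be separated from a period effect; the size of the bias is unknown and the carry-over part is probably small

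*Protocol*

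**What the plan says.** The effect of food on CORT125281 PK is a secondary objective (Protocol Section 2.2). Protocol Section 3.1.2 sets the design: "The effect of food on the PK of CORT125281 will be evaluated in 10 patients enrolled to the Abi-Resistant Cohort". The schedule is "Day -7: Single oral dose of CORT125281 administered under fasting conditions" and then "Day 1: Single oral dose of CORT125281 administered 30 minutes after a standard breakfast". Table 5 in Section 5.3.3 shows no CORT125281 from Day -6 to Day -1. SAP Section 2.4 repeats the same order. Section 5.11.1, covering Segment 1 and the Expansion Phase, states: "No randomization or allocation methods will be used in these parts of the study".

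For the analysis, Protocol Section 9.5.7 says that log-transformed Cmax and AUC "will be analyzed by analysis of variance (ANOVA) adjusted for food effect and other potential factors that may influence the outcome". Lack of a substantial food effect is inferred if the 90% CIs lie within 0.80 to 1.25. SAP Section 11 compares fed with fasted "using unadjusted and adjusted linear regression models that control for potential confounders". Neither document names period, sequence or carry-over.

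The plan does contain some protection. There is a 7-day gap, enzalutamide is held until Cycle 1 Day 2 in this subcohort, and Table 22 schedules a pre-dose sample on Day 1. No rule says how that sample will be used.

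**The concern.** With one order for everyone, anything that differs between the first and second dosing day is counted as food. The protocol delays enzalutamide precisely to keep this comparison clean, but it leaves the order of the two conditions uncontrolled.

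The documents give reasons not to take the period effect as zero. In Study CORT125281-600, on repeated dosing, "a slower terminal elimination phase became apparent" (Protocol Section 1.3.2.1). The drug is metabolised mainly by CYP3A4, inhibits it in vitro and may induce it (Section 1.3.1.3.3). The washouts for abiraterone, glucocorticoids and strong CYP inhibitors or inducers in Section 4.2 are counted back from the first CORT125281 dose. Here that is Day -7, so the fasted day is always a week nearer to prior therapy.

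At stake is the conclusion against 0.80–1.25. An upward shift in period 2 could hide a real fall in AUC with food, or make an unchanged AUC look raised. A downward shift would do the reverse.

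**Working it through.** **No plan figure to reproduce.** The documents state no power or precision for the 10-patient comparison.

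**1. Can food and period be separated?** Write ln(PK) = patient + food + period + error. That is 10 patient columns, one food column and one period column, 12 in all.
- Planned single order: rank 11 of 12. Food and period are the same column.
- 5:5 two-order crossover: rank 12 of 12.

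With no true food effect, an imposed period ratio of 1.05, 1.10 or 1.15 gives an estimated fed/fasted ratio of exactly 1.05, 1.10 or 1.15 in the planned design. In the 5:5 design it gives 1.00.

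**2. How much drug could remain?** Day -7 to Day 1, with no Day 0, is 7 × 24 = 168 h. The only human input is the 2- to 4-fold rise in exposure over 14 days of QD or BID dosing (Section 1.3.2.1). One-compartment reading: R = 1/(1 − e^(−kτ)), so the fraction left at 168 h is (1 − 1/R)^(168/τ).

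| Accumulation R | Interval τ | Half-life | Residual at 168 h |
|---|---|---|---|
| 2 | 12 h | 12 h | 0.5^14 = 0.006% |
| 4 | 12 h | 29 h | 0.75^14 = 1.8% |
| 2 | 24 h | 24 h | 0.5^7 = 0.8% |
| 3 | 24 h | 41 h | 0.667^7 = 5.9% |
| 4 | 24 h | 58 h | 0.75^7 = 13.3% |

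Section 1.3.2.1 places the greatest accumulation at 240 mg BID. The 4-fold end therefore belongs with τ = 12 h and about 1.8%, and the last row does not fit the source. QD accumulation was below the maximum by an unstated amount; 2- to 3-fold gives about 1–6%.

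**3. What does a shift do to the conclusion?** Within-patient CV is not given, so 20%, 25% and 30% are assumed. The 10 within-patient log differences are drawn from a normal distribution with mean ln(true ratio × (1 + shift)) and variance 2·ln(1 + CV²). A 90% t-interval on 9 degrees of freedom is formed, and intervals wholly inside 0.80–1.25 are counted (400,000 replicates). Treating the residual as a proportional shift in the ratio is itself an approximation.

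True ratio 0.80, so an interval inside the limits is a wrong inference of no food effect:

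| Shift | CV 20% | CV 25% | CV 30% |
|---|---|---|---|
| 0 | 4.9% | 4.1% | 2.6% |
| 1.8% | 7.1% | 5.3% | 3.2% |
| 5% | 12.3% | 8.1% | 4.5% |
| 10% | 23.8% | 13.4% | 6.4% |

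True ratio 1.00 at CV 20%: the chance of correctly landing inside is 0.51 with no shift, 0.50 at 1.8%, 0.46 at 5% and 0.34 at 10%.

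**4. Cmax against AUC.** In three subjects in Study 600, fed Cmax was about 47% lower (ratio about 0.53) and AUC was similar. Lifting 0.53 to 0.80 would need a period ratio of 0.80/0.53 = 1.51. A Cmax effect of that size is unlikely to be hidden; an AUC ratio near a limit could be.

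**The case against.** The strongest reply is that the bias is immaterial. The slow terminal phase and the accumulation come from 14 days of repeated dosing with greater-than-dose-proportional concentrations, so a linear back-calculation to a single dose is doubtful. The early data summarised in Protocol Section 1.5.2 showed dose-proportional exposure and led to a prediction of minimal accumulation. That prediction was later exceeded on repeat dosing, but a single dose followed by six dose-free days may leave almost nothing. Both days fall within about a week in the same patients, and enzalutamide is held until Day 2. The Expansion regimen is already specified as fed, so this result does not decide food conditions in this trial. The only earlier AUC result showed similar exposure fed and fasted.

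Most of this stands as an argument about size. It does not touch the aliasing, which follows from the schedule whatever the half-life.

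A reader might also infer four stronger things that the documents do not support:
- That 13% of the first dose carries over. This needs 4-fold accumulation on QD dosing, whereas the protocol puts the greatest accumulation at a BID dose.
- That the false-conclusion rate reaches about 24% or more. This needs an assumed period shift of 10% or more, and no documented cause of that size is identified.
- That the bias can only raise the fed profile. This holds for residual drug; CYP3A4 inhibition or induction has no documented single direction.
- That the missing period term is itself the defect. The open-ended model wording could admit one, but with a single order it cannot be estimated.

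**Conclusion.** The point holds as a design limitation. Food and period are completely aliased, so the planned ratio is food times period, and no choice of covariates can rescue it.

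The magnitude is uncertain and, as far as carry-over goes, probably small: about 1.8% or less on the reading that best fits the protocol, and about 1–6% if QD accumulation was 2- to 3-fold. At CV 20% and a true ratio of 0.80, that moves the false no-food-effect rate from about 5% to 7% at a 1.8% shift, and to 12% at 5%. The increase is smaller at higher CV. These figures rest on an assumed CV, a one-compartment model and an assumed true ratio at the limit. Period effects other than residual drug have neither a size nor a direction in the documents. The AUC conclusion is the one exposed. The change is worth making because it is cheap, not because a large bias has been shown.

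**What to change.** **Preferred.** Allocate the 10 patients at random, 5:5, to fasted-then-fed or fed-then-fasted on Day -7 and Day 1. Amend Protocol Section 5.11.1 and the descriptions in Sections 3.1.2, 5.3.3 and 5.10.2 and in SAP Section 2.4. In Protocol Section 9.5.7 and SAP Section 11, fit ln(Cmax) and ln(AUC) with sequence, period, food and patient terms. Carry-over that is equal after either condition then falls into the period term; carry-over that differs between conditions would still not be separable.

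**Cost.** A 10-line allocation list and the model wording, with no added visits or samples. Error degrees of freedom fall from 9 to 8; at CV 20% with no food effect, the chance of an interval inside the limits is 0.50 instead of 0.51. The Day 1 4-hour gene-panel sample, planned as not fasted in Table 19, would be fasted in five patients and must be flagged.

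**If the fixed order is kept.** Pre-specify a sensitivity analysis using the Day 1 pre-dose concentration, with a threshold for correction or exclusion that the sponsor justifies, and report the ratio as food plus period. This costs only SAP wording, but it addresses carry-over and no other period effect.

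**In either case.** The Table 22 note has CORT125281 and enzalutamide taken together on all PK days, while Sections 3.1.2 and 5.3.3 give no enzalutamide on Day 1 in this subcohort. These must be reconciled, because enzalutamide on that day would add another difference confined to the second period.
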